### Subsequent assessments and procedures

At visit 1, each participant and their parent(s), will be seen by the researcher who will make a global assessment of the participant and use the Childhood Autism Risks from Genetics and the Environment (CHARGE) Gastointestinal History Questionnaire (GIH) and a dietary assessment as pro-forma for interview and assessment. The parents will complete a questionnaire pack that consists of:

- A clinical assessment form recording basic demographic details, medical history, birth details, details about the mother's health in pregnancy and information on whether certain medical conditions are present in family members.
- Autism Treatment Evaluation Checklist (ATEC)
- Aberrant Behaviour Checklist (ABC)
- Autism Parenting Stress Index questionnaire.

After visit 2, if the participant tolerated the taste, the child's educator will be sent a letter inviting them to participate in the study with a consent slip to complete and return. Included with this letter will be;

- Parent Information Sheet
- Baseline questionnaire pack for the child's educator to complete in respect of the child
- Midpoint questionnaire pack for the child's educator to complete in respect of the child
- Final questionnaire pack for the child's educator to complete in respect of the child
- 3 stamped addressed envelopes for returning the questionnaires and consent slip
- provided.

The educator questionnaire packs consists of an Autism Treatment Evaluation Checklist and Aberrant Behaviour Checklist

The researcher will phone the participant's parent in Week 5 and Week 9. During the phone calls in Week 5 and Week 9, questions will be asked of the participant's parents to assess and encourage compliance and to check for any change in circumstances that might affect treatment efficacy.

After 12 weeks, there is a 4-week washout period during which the participants will attend UCLH for a 45-minute outpatient consultation (Visit 3). During this consultation, the researcher will make a global assessment and assess the frequency of GI symptoms using the GIH questionnaire. The participant's parents will again complete an ATEC and ABC evaluation for their child, and an Autism Parenting Stress Index questionnaire.

The researcher will phone the participant's parent in Week 21 and Week 25. During the phone calls in Week 21 and Week 25, questions will be asked of the participant's parent to assess and encourage compliance and to check for any change in circumstances that might affect treatment efficacy. Qualitative data on their experience of the trial will also be collected by the researcher.

After 29 weeks, participants will attend UCLH for a 45-minute outpatient consultation (Visit 4). They will be asked to bring any remaining Vivomixx/placebo sachets to the consultation. During this consultation, the researcher will make a global assessment and assess the frequency of GI symptoms

using the GIH questionnaire. The participant's parent will again complete an ATEC and ABC evaluation for their child, and an Autism Parenting Stress Index questionnaire.

Both groups will have the same amount of health professional contact.

The placebo's packaging, taste and appearance of the powder will be indistinguishable to Vivomixx.

### Discontinuation/withdrawal of participants

In consenting to participate in the trial, participants are consenting to intervention, assessments, followup and data collection.

A participant may be withdrawn from trial whenever continued participation is no longer in the participant's best interests, but the reasons for doing will be recorded. Reasons for discontinuing the trial may include:

- Participant's withdrawing consent
- Intercurrent illness
- Persistent non-compliance to protocol requirements

The decision to withdraw a participant from treatment will be recorded in the case report form (CRF) and medical notes. If a participant explicitly states they do not wish to contribute further data to the trial, their decision will be respected and recorded in the CRF and medical notes.

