#### Primary outcome analysis

The intention-to-treat (ITT) analysis will be performed on all participants who are randomised. An additional analysis will be done on only those participants who complete the study per protocol analysis.

Change in the ATEC score during follow-up will be examined using the mixed model for analysis of variance to account for missing data (dropouts). This model allows the evaluation of the effect of each factor on the outcome as well as the interactions between factors. The mixed model will use group (treatment ASD - vivomixx protocol v6.docx, IRAS 204582, Version 6.0, 30/01/2020, Page 43 of 57

versus control) and time as factors. If residuals prove not to be normally distributed, the Bonferroni multiple comparisons with Bootstrap multiple comparisons to accommodate for the non-normality of residuals will be done. A P-value <0.05 is considered significant and multiple comparisons will be undertaken with Fisher's least significant difference test and 95% confidence intervals.

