#### Sensitivity and other planned analyses

Sensitivity analysis of data outliers will be presented by showing data as box-plots.

Non-adherence to the protocol will be handled by performing intention to treat and per protocol analyses as necessary.

Missing data will be handled by inputting the missing data and redoing the analysis.

Data will be analysed for normality, and those which are not normally distributed will be non-parametrically assessed.

A more detailed statistical analysis plan will be produced prior to the final analysis. The plan will be reviewed and possibly updated as a result of the blind review of the data and will be finalised before breaking the blind. Formal records should be kept of when the statistical analysis plan was finalised as well as when the blind was subsequently broken.

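### The protocol allows withdrawal from the trial for non-compliance or illness without requiring the scheduled ATEC afterwards, so outcomes needed for the intention-to-treat analysis may be lost

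*Protocol*

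**What the plan says.** **Withdrawal.** Protocol, Discontinuation/withdrawal of participants: "A participant may be withdrawn from trial whenever continued participation is no longer in the participant's best interests". Among the reasons for discontinuing the trial are intercurrent illness and "Persistent non-compliance to protocol requirements"; the word persistent has no threshold. The same section then changes its object from the trial to the product: "The decision to withdraw a participant from treatment will be recorded in the case report form (CRF) and medical notes". It treats refusal of data as a further step: "If a participant explicitly states they do not wish to contribute further data to the trial, their decision will be respected". It opens by saying that "participants are consenting to intervention, assessments, followup and data collection".

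**Analysis in the protocol.** Primary outcome analysis: "The intention-to-treat (ITT) analysis will be performed on all participants who are randomised", with change in ATEC examined "using the mixed model for analysis of variance to account for missing data (dropouts"). Sensitivity and other planned analyses adds: "Missing data will be handled by inputting the missing data and redoing the analysis". No method is named.

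**Analysis in the SAP.** Principal Analysis tests between-phase differences with a paired t-test or a Wilcoxon signed-rank test. The SAP defines no intention-to-treat set and gives no missing-data rule. Its section on adherence and deviations only counts withdrawals and losses by phase.

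**Entry to period 2.** Protocol, Trial Design and Methods Summary, makes only children who complete all 12 weeks of period 1 eligible for period 2.

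**The concern.** Non-compliance and illness arise after randomisation, and either can be related to the product being taken. The protocol's own risk table expects temporary loose bowel motions with Vivomixx in 1 in 10. If leaving the trial for such a reason also ends the ratings, the missing scores are not missing by chance, and the set analysed differs from the set randomised.

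Intention to treat depends on collecting outcomes whether or not the product is taken. A promise to analyse every randomised child cannot be kept if the protocol lets the team take a child out of the trial and does not ask for the later scores. At stake is whether the reported ATEC difference describes all children allocated or mainly those who stayed on the product.

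**Working it through.** **1. What data a withdrawn child would have.** ATEC is scheduled three times: at the start, at Visit 3 in the washout, and at Visit 4 at the end (Protocol, Appendix 1). If visits stop at withdrawal:

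| Withdrawn | ATEC available | Protocol mixed model on change | SAP paired test |
|---|---|---|---|
| Before Visit 3 | Baseline only | No post-baseline score to use | Dropped |
| Between Visit 3 and Visit 4 | Baseline and Visit 3 | Kept, one phase | Dropped |
| Stops product, both visits kept | All three | Kept | Kept |

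The mixed model thus rescues only the second row, and the paired test neither of the first two. In the third row one matter is open. A child who did not complete period 1 may not enter period 2, so the Visit 4 score would follow no second treatment, and neither document says how to use it.

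**2. The plan's own figures.** Sample size calculation gives 82 enrolled, dropout of 15% in one sentence and 10% in another, 74 analysed, dz = 0.34, two-sided 5% and 80% power.
- 82 × 0.90 = 73.8, so 74.
- Power from the noncentral t distribution, with effective n = 74 × 3/π for the Wilcoxon test, is 0.805 (paired t: 0.823). The stated 80% is reproduced.

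The stated power therefore already rests on about 74 complete pairs rather than 82 children. The documents do not split the dropout by cause.

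**3. Possible size of the bias (illustration).** Let p be the share of randomised children withdrawn by the team and lost. Assume they have zero effect, and that the children who remain show the plan's 15-point difference.
- All-randomised difference = 15 × (1 − p).
- Overstatement factor = 1 / (1 − p).
- Diluted dz with all 82 followed = 0.34(1 − p) / √(1 + 0.34² p(1 − p)).

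| p | All-randomised difference | Factor | Remaining n, power (paired t) | All 82 followed: dz, power |
|---|---|---|---|---|
| 0 | 15.00 | 1.00 | 82, 0.86 | 0.34, 0.86 |
| 0.05 | 14.25 | 1.05 | 78, 0.84 | 0.32, 0.82 |
| 0.10 | 13.50 | 1.11 | 74, 0.82 | 0.30, 0.78 |
| 0.15 | 12.75 | 1.18 | 70, 0.80 | 0.29, 0.73 |

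The last two rows treat the whole planned dropout as team withdrawal. The p = 0.05 row corresponds to half of a 10% dropout. The lower power in the right-hand column reflects a smaller effect in all randomised children, not a loss of information.

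**4. Direction.** The table assumes that those lost have no effect, which makes the reported difference too large. If children were instead withdrawn while doing badly in the placebo phase, poor placebo scores would go missing and the difference would be too small.

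**The case against.** The best defence is that the withdrawal section, read as a whole, implies that data continue. Consent covers follow-up and data collection, a decision to withdraw from treatment is recorded as such, and refusing further data is a separate, explicit act. Withdrawal is discretionary and framed by the child's best interests. Illness need not end participation: under Concomitant medication, children prescribed antibiotics may carry on. Interview study methods plans an in-person contact on exit, among contacts where outcome measures are collected. Retention measures are listed, and non-adherence is to be handled by both intention-to-treat and per-protocol analyses.

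Much of this stands. A reader might infer that outcomes are certain to be lost and that the main analysis becomes one of compliers. The documents do not say that; they leave it possible. A reader might also infer that the team could remove children who respond poorly to the active product. Poor response is not a listed reason, and allocation is concealed from the researcher. Nor is taste a convincing product-related route, since the placebo is matched and a taste week comes first. Loose bowels are described as short-lived.

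What the defence does not supply is an instruction. Continued data collection is an inference, while the listed event is leaving the trial, and a site could reasonably stop the visits. An exit interview is not a rating at the scheduled time, and ATEC at exit is not expressly required. The retention measures chase late questionnaires and do not mention children whom the team has withdrawn.

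**Conclusion.** The point holds as a gap that conflicts with the promised analysis, not as a demonstrated loss of data. Withdrawal from the trial for non-compliance or illness is permitted, no text requires the scheduled ATEC afterwards, and the protocol promises to analyse every randomised child. The main routes from that gap to a complete-pair analysis are the SAP's paired test and the completers-only entry to period 2.

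The size cannot be derived from the documents. It is 0% if no loss is of this kind. It reaches an overstatement of 11–18% only if every planned dropout is a team withdrawal and those children have zero effect. Reading 11–18% as an expected bias would be wrong: the 10–15% is total dropout, and it includes families who withdraw consent, whose data would be lost under any wording. The direction is also uncertain. The matter should be corrected because the remedy is cheap; confidence that it would change the result is moderate at most.

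**What to change.** 1. **Protocol, Discontinuation/withdrawal of participants.** Define two events. Stopping the product remains a clinical decision, for whatever reasons apply now, and does not end follow-up. Leaving follow-up happens only when consent for data is withdrawn.
2. **Outcome collection.** Ask families of children who stop the product for any other reason to complete ATEC, ABC, APSI and GIH at the scheduled Visit 3 and Visit 4 times, by telephone if needed. Data collection tools and source document identification already allows telephone completion of questionnaires.
3. **Trial Design and Methods Summary.** Reconcile the completers-only entry to period 2 with this follow-up, and state how the Visit 4 score of a child who did not enter period 2 is used.
4. **SAP.** Define the intention-to-treat set. Analyse all randomised children with any post-baseline ATEC through the mixed model already promised in the protocol, and keep the paired test as a complete-pair sensitivity analysis. Name the imputation method, and report by sequence and phase how many children have no post-baseline score and why.

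The cost is mainly wording and some extra telephone calls. Some families will decline. The estimate may be slightly less favourable, and under the assumptions in the table the power with all 82 followed would be 0.73–0.82 rather than 0.80–0.84. If follow-up has already finished, item 4 is still possible.

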### **Definition of End of Trial**

The expected duration of the trial is 1 year from recruitment of the first participant. The end of the trial is the date of the last visit of the last participant.

# **Recording and reporting of adverse events**

### Definitions

Term	Definition	
Adverse Event (AE)	Any untoward medical occurrence in a patient or trial participant, which does not necessarily have a causal relationship with the intervention involved.	
Serious Adverse Event (SAE)	
 
Any adverse event that:
 
results in death,
 
is life-threatening*,
 
requires hospitalisation or prolongation of existing hospitalisation**,
 
results in persistent or significant disability or incapacity, or
 
consists of a congenital anomaly or birth defect.
 
	

\*A life-threatening event refers to an event in which the participant was at risk of death at the time of the event; it does not refer to an event which hypothetically might have caused death if it were more severe.

\*\*Hospitalisation is defined as an in-patient admission, regardless of length of stay. Hospitalisation for pre-existing conditions, including elective procedures do not constitute an SAE

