# **ASD and Co-morbid Conditions**

The most common co-morbid symptoms in young children with autism are sleep disruption (86%), hyperactivity, and gastrointestinal disorders (70%), followed by self-injurious behaviour (34%), aggression/irritability (22%), motor co-ordination and eating problems [14]. Research suggests that children with ASD are more likely to have health problems and illnesses in general compared to typically developing children.

There is an increased risk for epilepsy in autistic individuals and for some subgroups this is significantly higher. In autistic individuals with intellectual disability the prevalence is 21.5% and for those without intellectual disability it is 8% [15].

A longitudinal study in Sweden found the death rate in autistic individuals was a rate 5.6 times higher than expected. Associated medical disorders (including epilepsy with cognitive impairment) and accidents accounted for most of the deaths and it was not possible to determine whether autism per se actually carries an increased mortality risk [16].

In a 2014 survey of 264 parents of children with ASDs in the UK, they were asked about they main health challenges facing their children and their efforts to access services [10]. This report highlighted the scale of the challenges faced by children with ASD and their families including the following:

%	Challenge suffered by child
reporting	
85	Anxiety/fearfulness/avoidance behaviours
85	Irritability (low mood/tantrums/lack of flexibility/oppositional behaviours)
85	Sensory sensitivity
78	Lethargy or hyperactivity
78	Diarrhoea/constipation/highly abnormal bowel movements
72	Gastrointestinal symptoms (flatulence/bloating/posturing/seeking pressure on stomach)
57	Incontinence (urinary/bowel)

Their report [10] concluded that their survey highlighted the need for more scientific research into the causes and possible treatments of ASD as well as the range of co-morbid conditions associated with ASDs. It also reported how parental experiences of diet and nutritional supplements (such as probiotics) suggested that these can make a significant difference to the lives of children with ASD and warrant further research.

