# **Assessment and Management of Risk**

The ASD-Probiotic trial involves a treatment for children with autistic spectrum disorders who have gastrointestinal symptoms. It is well established in clinical practice that children with ASDs often present with these symptoms and adverse effects will be those observed in everyday practice associated with management of GI symptoms.

There are no tests being performed during the trial that are above standard care. The table below summarises the risks and mitigations of the intervention that are being performed in a table:

Intervention	Potential Risk	Risk Management
Oral age-related dose of Vivomixx probiotic	Allergic reaction	Those with a previous allergic reaction to any probiotic will be excluded from the study
Oral age-related dose of placebo powder containing maltose and silicon dioxide	Allergic reaction	The placebo contains maltose and silicon dioxide which has a very low allegenic profile
Oral age-related dose of Vivomixx	Temporary loose bowel motions	Participants are made aware of this possible temporary side effect which occurs in 1 in 10 patients and does not last typically beyond 2 days. Participants will be able to contact the research clinician at any time if they have concerns about this.

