# **Overall Study Flow**

# **Selection of Participants**

### **Inclusion criteria**

- Must have a diagnosis of ASD confirmed by a medical professional using one of the following standard assessment tools: Autism Diagnostic Interview – Revised (ADI-R), Diagnostic Interview for Social and Communication disorders (DISCO) or Developmental, Dimensional and Diagnostic Interview (3di).
- Have one or more gastrointestinal symptoms (constipation, diarrhoea, abnormal stools, pain on defecation, abdominal pain, gaseousness/bloating, reflux) for the past 6 months.
- Are either not taking any medication or have been on the same medication for the last 3 months.
- The patient or the patient's parents/guardian are willing and able to provide a written informed consent
- Be willing and able to continue with current medication or nutritional supplements throughout the 30-week trial.
- The patient's primary carer must be willing and able to complete the questionnaires at three time-points in the study. These questionnaires are only available in written English.
- Be willing to refrain from starting any kind of special diet for the duration of the study.
- Be between 3 years and 16 years of age

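### As written, an unplanned admission for worsening of a child's own entry GI symptom is not an SAE unless it is fatal, life-threatening or disabling

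*Protocol*

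**What the plan says.** In the protocol's Definitions table (Recording and reporting of adverse events), one of the five SAE criteria is that the event "requires hospitalisation or prolongation of existing hospitalisation". A footnote to that criterion has two sentences. The first is broad: "Hospitalisation is defined as an in-patient admission, regardless of length of stay". The second narrows it: "Hospitalisation for pre-existing conditions, including elective procedures do not constitute an SAE".

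The Inclusion criteria require that a child "Have one or more gastrointestinal symptoms (constipation, diarrhoea, abnormal stools, pain on defecation, abdominal pain, gaseousness/bloating, reflux) for the past 6 months". Assessment and Management of Risk lists "Temporary loose bowel motions" as a potential risk of the product, and says this "occurs in 1 in 10 patients and does not last typically beyond 2 days".

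The adverse event definition is wide: "Any untoward medical occurrence in a patient or trial participant, which does not necessarily have a causal relationship with the intervention involved". It does not mention worsening of a condition already present.

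The recording routes differ. Recording adverse events requires only the medical records in the first instance. The SAE procedures require the medical records, the case report form and the sponsor's AE log. The Trial Management Group section lists SAEs among the items that group reviews.

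**The concern.** The exclusion turns on whether the condition existed before, not on whether the admission was planned or the condition had worsened. That matters more here than in most trials, because a chronic GI symptom is the ticket of entry and the product's one listed bowel effect lies in the same organ system. The protocol expects adverse effects to resemble those seen when GI symptoms are managed in everyday practice. It then removes admission for a pre-existing condition from the hospitalisation criterion.

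What is at stake is how a foreseeable serious event is classified. Two people assessing the same admission could reach opposite answers, and a low count of serious GI events could partly reflect the wording rather than the children's experience.

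**Working it through.** This is a reading of the text. The plan states no figure to reproduce and no arithmetic applies.

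**Step 1: scope of the exclusion.** The footnote mark sits on the hospitalisation criterion alone. In the second footnote sentence, the word introducing elective procedures makes them one member of the excluded class and does not confine the class to them. The sentence has no condition on planning, timing or change in severity.

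**Step 2: who has a pre-existing condition.** The entry criterion asks for one or more of seven GI symptoms over the past six months. Each eligible child therefore has at least one such symptom at enrolment, but not necessarily more than one.

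**Step 3: apply the rule to three admissions.**

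| Unplanned admission during the trial | Status under the literal text |
|---|---|
| Entered with diarrhoea; admitted with worse diarrhoea; not fatal, life-threatening or disabling | Excluded from the hospitalisation criterion; no other criterion met; not an SAE |
| As above, but life-threatening or causing persistent or significant disability | SAE under another criterion, which the footnote does not touch |
| Entered with constipation only; admitted with new diarrhoea | Arguably not pre-existing; could be an SAE |

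The first row is the gap.

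**Step 4: look for a clause that closes it.** The places to look are the risk assessment, the protocol sections from Definitions to Trust Incidents and Near Misses, the Data Monitoring Committee section and the SAP's Safety Analysis. None says how an unplanned admission, or an admission for worsening, is to be classified. The SAE list also has no criterion for other medically important events that might catch it.

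**Step 5: what the event keeps and what it loses.**

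- *Kept:* it meets the wide adverse event definition. Assessments of Adverse Events requires every event to be assessed for severity, causality, seriousness and expectedness. The SAP's Safety Analysis compares adverse events between active and placebo phases by a relative risk with a 95% confidence interval, and this does not depend on SAE status.
- *Lost:* the serious label, the required entry in the case report form and sponsor's AE log, and the Trial Management Group's SAE review. The SAP gives no breakdown by seriousness, so in that analysis the admission would count the same as a mild event.

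**The case against.** The strongest reply is that the footnote is meant for planned care, that an experienced investigator would read it that way, and that the product is a low-risk food supplement whose listed bowel effect is short-lived. The intended meaning may well be planned care, but the sentence does not say so. Where every participant has a chronic GI symptom, the reading should not be left to the individual assessor.

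A second reply is that the event is not lost to the trial. This stands. It is still an adverse event, it can still be graded severe, and the Causality section's reference to completing the case report form suggests that adverse events may reach that form anyway. The loss is of classification and of the guaranteed SAE route.

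A reader might also infer more than the documents support:

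- *That the trial could not record a serious GI event at all.* The exclusion qualifies one criterion of five. Fatal, life-threatening or disabling worsening remains an SAE, and all deaths are recorded.
- *That all 82 planned children are at risk of a lost SAE.* Entry needs only one symptom, and a symptom new to that child is arguably outside the exclusion. The documents do not say how many children have an entry symptom that matches a plausible harm.
- *That the epilepsy prevalences under ASD and Co-morbid Conditions give a count of excluded seizure admissions.* They are prevalences of epilepsy, not admission rates, and seizures are not listed as a risk of the product.
- *That Data Monitoring Committee notification fails because of this sentence.* That route also requires the event to be related, unexpected and within 24 hours of a dose. Worsened diarrhoea might count as expected, so it could miss that route even after the wording is corrected.

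**Conclusion.** The point holds in a limited form. Under the literal definition, an unplanned admission for worsening of a child's own entry symptom is not an SAE unless it is fatal, life-threatening or disabling, and no other section brings it back. The event stays in the adverse event comparison but loses its serious status and the reporting that depends on it.

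This rests on two readings: that a chronic entry symptom counts as a pre-existing condition, and that elective procedures illustrate the exclusion rather than bound it. The second is plain from the grammar. The first is natural but not stated, since the Inclusion criteria speak of symptoms and the footnote of conditions.

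No size can be put on it. The documents give no rate of admission for GI symptoms, and the 1 in 10 figure for temporary loose motions is not such a rate. The case for change is that the event is foreseeable in this population and the correction is cheap.

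**What to change.** Replace the second sentence of the footnote with wording such as: *Planned or elective admission for a condition present at enrolment that has not worsened does not constitute an SAE; unplanned admission, or admission for worsening of a pre-existing condition, does.* Add to the adverse event definition that worsening of a pre-existing condition is an adverse event.

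The investigator should judge worsening against the child's recorded status before the treatment period in question, using the medical history and the most recent GI History. For the second period, that is the Visit 3 GI History rather than the Visit 1 one. GI History frequency should not decide it alone: the Secondary Outcomes section describes the tool as a frequency assessment and says severity is hard to assess in these children, so a more severe episode at unchanged frequency could be missed.

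If follow-up has ended, the same rule can be applied by reviewing admissions in the medical records, preferably by someone blind to treatment period.

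The cost is one amended sentence, one added line, a note on the SAE form, and a few more SAE forms in a population with chronic symptoms. No outcome, sample size or planned analysis changes.
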